Chitosan has been extensively tested in human for indications related to obesity, glucose control, hypertension, renal failure, and the metabolic syndrome. Table 1 is a partial selection of trials that can be found in the published literature. These studies include 371 patients treated with oral chitosan, in doses up to 5,250mg daily, and for periods of up to 1 year. These doses include the range of proposed dosing in our study. A variety of benefits were claimed. No study reported SAEs or significant (grade 3,4) AEs. When reported, compliance was generally high, and in randomized studies, was similar between the chitosan and placebo arms. Described AEs

predominately included GI complaints (constipation, bloating, full feeling, gas) but these were also described in the placebo arms. Where attribution was made, constipation was described as “not related” to the study drug. Three studies made no comment on chitosan toxicity. While the toxicity in these studies may be unclear, it is unlikely that the chitosan intervention was highly toxic. (58,62-72)

Table 1. Toxicity of Chitosan in Humans

disease	study type	chitosan	placebo	chitosan dose	duration	effects	toxicity	ref
renal Dz on dialysis	randomized	40	40	1350mg/d vs placebo	12 wks	lower creatinine, cholesterol; improved Hb, wt	"no clinically problematic symptoms"	1
elderly	single arm	18	18	5100mg/d	8 wks	immune cytokine increase	"no safety problems"	2
high cholesterol	crossover	65	65	2400mg/d vs placebo	3 months	no reduced chol, ApoE	no SAEs. Reported AEs were mild (GI complaints, pains, swelling, rash, heart palpitation, insomnia). 7/65 (chito) vs 5/65 (placebo) dropouts	3
high cholesterol women	randomized	46	44	1200mg/d vs placebo	56 days	lowered chol	few; no SAE; 4/46 AE in chitosan (thirst x 3, aphthous ulcer x 1), 2/44 AE in placebo (abd fullness, HA)	4
healthy males	single arm	7		5,250mg/d	12 days	no reduced fat absorption	no comment	5
healthy adult	randomized (chitosan vs orlistat)	6	6	2670mg/d	21 days	no increase in fat excretion	"well-tolerated, with no subjects reporting SAEs or discontinuing study. Majority of AEs were gastrointestinal in nature, reported by 8% of subjects on chitosan"	6
adult	randomized	44	44	1000mg/d vs placebo	112 days	no reduced wt or body fat	72.3% completed study	7

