3.2 Exclusion Criteria

1. Known allergy to chitosan or shellfish.
2. History of receiving more than 2 classes of ADT.
3. Chronic constipation (BM < 3 x weekly), history of malabsorption or history of daily laxative use.
4. Patients requiring medication administration with lunch or dinner or at a frequency of three or more times per day are not eligible.
5. Current use of chitosan, sevelamer, and/or glucosamine.
6. Patients currently on diclofenac or any of the restricted therapies listed in section 4.5

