4.2 Chitosan administration

Subjects will be enrolled sequentially into four cohorts; the starting dose level is cohort 1. These cohorts will take chitosan as described in Table 2. Three patients will be enrolled into cohort 1, and no patients will be enrolled into the next cohort until the final patient in cohort 1 will have completed 28 days of treatment.

Chitosan will be taken up to 30 minutes before, or during, the middle and evening meals (BID dosing) or the largest meal of the day (Q day dosing). Chitosan will not be taken with breakfast, and the subjects should endeavor to take any chronic medicines before or with breakfast to minimize the chance of absorption of pharmaceuticals to chitosan. Any pharmaceuticals should be taken at least 1 hour before or 2 hours after chitosan. Any chitosan doses lost through vomiting will not be made up.

Cohort	Chitosan
-1	500mg Q day
1	500mg BID
2	1000mg BID
3	1500mg BID
4	2000mg BID

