4.4 Discontinuation of Therapy

Participation in this study should be discontinued for any of the following reasons:

- Change in anti-cancer therapy
- Procedures requiring general anesthesia.
- Development of any medical condition that, in the opinion of the treating physician, requires discontinuation of the study intervention
- Withdrawal of consent by the subject
- Evidence of allergic reaction to any component of the treatment regimen
- Any grade 3-4 hematologic or non-hematologic toxicity (other than in 4.5) that does not resolve, with drug discontinuation, to grade 1 or less in 14 days.

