6.1.1 Supply

Chitosan will be provided in 500mg capsules. Chitosan will be stored at the investigational pharmacy located at each participating center. Chitosan will be distributed by the investigational pharmacy at each participating center. Due to COVID-19 restrictions Chitosan can also be mailed to the subject directly. It will be purchased from an external supplier and repackaged by the investigational pharmacy at each participating center. The packaging will include the label information required per 21 CFR part 312.

6.1.2 Storage.

The capsules should be stored at a controlled room temperature, with excursions to 15-30°C (59-86°F) permitted. All capsules should be kept in a secured storage area.

6.1.3 Administration.

See section 4.2 for chitosan administration instructions.

6.1.4 Known Potential Toxicities.

Patients with allergies to any shellfish should not take Chitosan as it can cause anaphylactic shock. Known toxicities of chitosan include included flatulence, increased stool bulkiness, bloating, mild nausea, and heartburn. Chitosan may interfere with how your body absorbs some medications, including certain beta blockers (propranolol), blood thinners (warfarin), diuretics (thiazides), cholesterol medications (zetia), diabetes medications (rosiglitazone), and antibiotics (ciprofloxacin). It is important that you take the study drugs as instructed by the study doctor to avoid any possible drug interactions.

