8.2 Reporting of SAEs

Following the subject's registration, all SAEs should be collected and reported, including those thought to be associated with clinical trial procedures. SAE terminology and severity grading will

be based on CTCAEv4. The following categories and definitions of causal relationship to study drug should be used:

- Definitely related: An adverse event occurring in a plausible time relationship to drug administration, and which cannot be explained by concurrent disease or other drugs or chemicals. The response to withdrawal of the drug should be clinically plausible. The event must be definite pharmacologically or phenomenologically, using a satisfactory rechallenge procedure if necessary and feasible.
- Possibly related: An adverse event with a reasonable time sequence to administration of the drug, but which could also be explained by concurrent disease or other drugs or chemicals. Information on drug withdrawal may be lacking or unclear.
- Not related: An adverse event with a temporal relationship to drug administration which makes a causal relationship improbable, and in which other drugs, chemicals or underlying diseases provide plausible explanations.

Adverse events classified as “serious” require expeditious handling and reporting to the coordinating center and Sponsor-Investigator. SAEs must be reported to all of these entities within 24hrs of becoming aware of the event, *whether or not the event is related to the study drugs or procedures*. If only limited information is initially available, follow-up reports are required. The original SAE form must be kept on file at the study site.

SAEs should be reported on the 102898 SAE eCRF via REDCap at redcap.musc.edu. The coordinating center will be responsible for submission to the Sponsor-Investigator, HCC-DSMC and FDA as applicable. SAEs should be reported to the site’s IRB per institutional standards.

The site should receive confirmation from MUSC that the SAE report was received. If not, please contact the SIS Unit immediately.

Collection of complete information concerning SAEs is extremely important. Thus, follow-up information which becomes available as the SAE evolves, as well as supporting documentation (e.g., hospital discharge summaries and autopsy reports), should be collected subsequently, if not available at the time of the initial report, and immediately sent using the same procedure as the initial SAE report.

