10 STATISTICAL METHODS AND POWER ANALYSIS

10.1 Escalation Design

The investigators will use a 3+3 design for assignment to cohorts. The cohorts are shown in Table 3. An initial 3 subjects will be enrolled at dose level 1. Dose-limiting toxicities (DLT) will be defined only in the first 28 days of therapy. If there are no DLTs after the final patient has been treated for 28 days, then the next cohort will be enrolled in dose level 2, and so forth. If a DLT occurs, then 3 more subjects will be enrolled into that cohort. If two DLTs occur in the first 3 patients in a dose level, then dose will be de-escalated and 3 additional patients will be enrolled in the lower dose

Dose Level	Chitosan	number
-1	500mg QD	3 (+3)
1	500mg BID	3 (+3)
2	1000mg BID	3 (+3)
3	1500mg BID	3 (+3)
4	2000mg BID	3 (+3) +30

level unless 6 have already been treated at that dose level. The MTD will be defined as the dose at which no more than 1 out of 6 subjects experiences a DLT.

Definition of DLT:

- Grade 3 or higher hypophosphatemia
- Grade 3 or higher of any of the following toxicities, that the investigator deems related to chitosan, that do not improve or resolve within 7 days of onset: flatulence, increased stool bulkiness, bloating, nausea, heartburn

10.2 Expansion Cohort Design and Statistical Analysis.

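### The DLT definition is a closed list, so any other chitosan-related grade 3+ event in days 1–28 adds nothing to the 3+3 count or the MTD

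*Combined protocol and SAP*

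**What the plan says.** Section 2.2 makes the MTD the primary objective and defines it as a dose with no more than 1 DLT in 6 subjects. Section 10.1 uses a 3+3 design with a 28-day DLT window. A DLT is one of two things:

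- hypophosphatemia of grade 3 or above, with no condition on attribution or duration;
- one of "flatulence, increased stool bulkiness, bloating, nausea, heartburn", if it is grade 3 or above, judged related to chitosan, and not improved or resolved within 7 days.

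Escalation, cohort expansion, de-escalation and the MTD all depend on that count alone. No wider definition appears in sections 2.2, 4.4, 7.4, 8, 9 or 10.

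Other sections mention events that are not on the list. Section 6.1.4 warns: "Patients with allergies to any shellfish should not take Chitosan as it can cause anaphylactic shock". Section 4.2 says: "Any chitosan doses lost through vomiting will not be made up". Section 4.4 ends participation for "Evidence of allergic reaction to any component of the treatment regimen". It also ends it for "Any grade 3-4 hematologic or non-hematologic toxicity" that does not settle to grade 1 or less within 14 days of stopping the drug. Neither stop in section 4.4 is tied to the DLT count.

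**The concern.** Section 2.1 sets the goal as a safe dose. A dose-finding rule that counts only tolerability effects already known for the agent cannot respond to anything else. Suppose one of three patients at a level has a related grade 3 allergic reaction on day 10. Section 4.4 removes him, yet no DLT is recorded, and if nothing else happens the rule in section 10.1 sends the next cohort to a higher dose. The same holds for severe related vomiting, for constipation, and for a related death that does not arise through a listed event. The stop for the individual and the decision about the dose are not connected, and the dose decision is the primary result.

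**Working it through.** The plan gives no operating characteristics for the escalation, so there is no figure to reproduce. Its stated power of 0.88 belongs to the AGE endpoint and has no bearing here.

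**1. What counts.**

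| Related grade 3+ event, days 1–28 | On the 10.1 list? | What the plan does |
|---|---|---|
| Nausea lasting more than 7 days | Yes | Counts as a DLT |
| Allergic reaction | No | 4.4: patient stops |
| Vomiting | No | 4.2: lost dose not replaced; 4.4 if unresolved at 14 days |
| Constipation | No | 4.4 if unresolved at 14 days |
| Death not through a listed event | No | 8.2: SAE report |

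A death graded as hypophosphatemia, or one that follows a listed symptom meeting all its conditions, would still count.

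**2. What the cited trials can exclude.** Of them, section 1.6.4 says: "No study reported SAEs or significant (grade 3,4) AEs".

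- The chitosan column of Table 1 sums to 40+18+65+46+7+6+44+15+10+50+64+6 = 371.
- Three studies make no comment on toxicity: 7+10+6 = 23, leaving 348.
- A 44-patient study gives only a completion rate, leaving 304.
- With 0 events in 304, the one-sided 95% upper bound is 1 − 0.05^(1/304) = 0.0098, or 1.0%.
- Levels 3 and 4 give 2 × 1,500 = 3,000 and 2 × 2,000 = 4,000 mg/day. Stated doses of 3,000 mg/day or more occur in two studies: 5,100 mg (n = 18) and 5,250 mg (n = 7), 25 patients in all.
- The study of 7 makes no comment on toxicity. For 0 in 18 the bound is 1 − 0.05^(1/18) = 0.153, or 15%.

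The text also cites up to 6.75 g/day for 8 weeks without significant effects, but gives no patient number.

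**3. Effect of counting the events.** Let q be the chance that a patient has an unlisted grade 3+ event in days 1–28 that is judged related. The documents give no value, so 1%, 2% and 5% are assumptions, and q includes misattributed events. Listed DLTs are set to zero to isolate the change. Under the closed list the chance of passing a level is then 1 whatever q is. If the events counted:

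- level expanded by 3 patients (exactly 1 of 3): 3q(1−q)²
- level passed (0 of 3, or 1 of 3 then 0 of 3): (1−q)³ + 3q(1−q)⁵
- at least one event in 6 patients: 1 − (1−q)⁶

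At q = 0.05 the pass probability is 0.857375 + 0.116067 = 0.973442.

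| q | At least one in 6 | Level expanded | Level passed | Fall (points) | All four levels passed, same q | Fall (points) |
|---|---|---|---|---|---|---|
| 1% | 5.9% | 2.9% | 0.9988 | 0.1 | 0.9953 | 0.5 |
| 2% | 11.4% | 5.8% | 0.9954 | 0.5 | 0.9818 | 1.8 |
| 5% | 26.5% | 13.5% | 0.9734 | 2.7 | 0.8979 | 10.2 |

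Purely to show what the rule cannot see: at q = 33% the pass probability would be 0.43 if the events counted, against 1.00 under the closed list. Nothing in the documents supports such a rate.

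**4. Sample size.** With every level expanded and 27 patients added at the MTD, 4 × 6 + 27 = 51, within the maximum of 54.

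**The case against.** The list has a visible logic. Its five symptoms are the known toxicities in section 6.1.4, and hypophosphatemia fits the phosphate binding described in section 1.6.2. For a supplement on open sale, a tolerability definition is understandable. That explains the list, but it does not show that a related event outside it should leave the dose decision unchanged.

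A reader might infer that the protocol expects anaphylaxis in its own patients. It does not: the warning concerns people with shellfish allergy, and section 3.2 excludes "Known allergy to chitosan or shellfish". What remains is a first reaction in a patient with no known allergy. Likewise, the vomiting sentence is a missed-dose instruction and predicts nothing about severe vomiting. Constipation has somewhat more behind it: one Table 1 trial reports 6/15 on chitosan against 2/15 on placebo. But no grade 3 case is reported, section 1.6.4 says constipation was judged unrelated where attribution was made, and chronic constipation is excluded.

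A reader might also infer that a death could pass unnoticed. That is not so. Under section 8.2, "SAEs must be reported to all of these entities within 24hrs of becoming aware of the event". Section 9.1 provides monthly committee review of IRB-reportable serious events, with authority to recommend suspension or closure. This is a real protection and could halt the trial whatever the DLT count. It is discretionary, however, and does not change the count or the definition of the MTD.

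Finally, it is tempting to carry the event rates through to everyone treated at the MTD. That would not measure this gap. The 27 expansion patients enrol after the MTD is set, and a wider definition in section 10.1 would not make their events count towards it.

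**Conclusion.** The gap is real and lies in the rule that produces the primary result: a chitosan-related grade 3+ event outside the list does not affect escalation or the MTD. It is worth correcting because the change is cheap. The expected practical effect is small. The cited trials report no grade 3–4 events, and the 1.0% upper bound, which rests mostly on lower doses, lies well below the 5% scenario. The information at the doses of levels 3 and 4 is too thin to bound the rate usefully, but thin data are not evidence of toxicity, and nothing here shows that chitosan is unsafe or that the trial will select a wrong dose. The probabilities rest on assumed rates, independent patients and no listed DLTs; the four-level figures also assume the same rate at every dose.

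**What to change.** Add a third entry to section 10.1: *any other adverse event of grade 3 or above with onset in days 1–28 that the investigator judges related to chitosan*. With it:

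- apply the existing 7-day improvement window to non-serious GI events such as vomiting and constipation, so that they are treated like the listed symptoms;
- count a grade 3+ allergic reaction, any related grade 4 event and any related death at onset;
- state that any related death pauses escalation until the DSMC has reviewed it. The catch-all alone would not do this: a single death is one DLT, and one DLT in six still meets the MTD definition.

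The text change is a few sentences. Clinical events need no new data collection, since adverse events are already graded (section 8.1) and asked about by telephone on days 14 and 29 (Appendix A, footnote g). Laboratory events are different. Appendix A schedules no CBC, CMP or phosphorus between day 1 and day 85, so without an added blood draw the catch-all will mainly capture clinical events.

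The price is some extra expansions and some risk of counting background illness in this population. At rates of 1%, 2% and 5%, true and misattributed events together, a level expands by 3 patients with probability 2.9%, 5.8% and 13.5%, which the planned 3 (+3) per level already allows for.

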2.2 Primary Objective

The primary objective is to determine the maximum tolerated dose (MTD) of chitosan in subjects with PCa on ADT. The MTD will be defined as the dose that produces no more than 1 dose-limiting toxicity (DLT) in 6 subjects.

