Once the MTD is established, 27 additional subjects will be recruited at that dose level to better define toxicity and changes in AGEs. The maximum number of patients that can be accrued is 54. The primary measure of change in AGE is defined as a binary indicator of a 30% or greater decrease in plasma total AGE level between baseline and day 85 specimens. The proportion of patients with a 30% or greater decrease will be calculated with its exact 95% confidence interval. An exact binomial test will be based on a null hypothesized true proportion of 0.25 (i.e., 25% of patients have a $\geq 30\%$ reduction in AGE levels) which is too low to be of further interest. With an alternative of 0.50 and 33 patients, assuming a 1-sided alpha of 0.05, the power is 0.88. Graphical displays will be made to demonstrate patterns in AGE between baseline and day 85. The following analyses will be performed, and then data will be stratified by race, and analyses repeated to evaluate differences by race. Summary statistics (mean change between timepoints, standard deviations, medians) will be reported. Scatterplots and paired t-tests will be used to compare the mean change between baseline and day 85 with a 2-sided alpha of 0.05 for changes in AGE levels and changes in other variables of interest (e.g. race, BMI). Linear regression will be used to evaluate associations between continuous variables and changes in AGE levels with changes in AGE levels as the outcome. Transformations will be taken as appropriate and residual plots will be examined to evaluate assumptions of linear regression model. The investigators will add baseline levels of clinical parameters in the linear regression model to account for starting levels. Regression coefficients will be evaluated in terms of clinical effect size and statistical significance. Model results will be reported with 95% confidence intervals.

REFERENCES

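### Expansion is 27 at the MTD in the Section 10.2 text but +30 at level 4 only in the Section 10.1 table, and no enrolment rule covers 0/3 at level 4

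*Combined protocol and SAP*

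**What the plan says.** Section 10.2 sets the expansion: "Once the MTD is established, 27 additional subjects will be recruited at that dose level". It then gives a ceiling, "The maximum number of patients that can be accrued is 54", and the power statement, "With an alternative of 0.50 and 33 patients, assuming a 1-sided alpha of 0.05, the power is 0.88". The test is an exact binomial test against a null proportion of 0.25.

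The dose table in Section 10.1 lists 3 (+3) for levels -1, 1, 2 and 3. For level 4 it lists 3 (+3) +30. No other row carries an expansion number.

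The enrolment rules in Section 10.1 are:

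- No DLT: "If there are no DLTs after the final patient has been treated for 28 days, then the next cohort will be enrolled", and so on up the levels.
- A DLT: "If a DLT occurs, then 3 more subjects will be enrolled into that cohort".
- Two early DLTs: "If two DLTs occur in the first 3 patients in a dose level, then dose will be de-escalated", with three more at the lower level unless it already has six.

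The MTD is defined on six subjects in both places where it appears. Section 2.2: "The MTD will be defined as the dose that produces no more than 1 dose-limiting toxicity (DLT) in 6 subjects". Section 10.1: "The MTD will be defined as the dose at which no more than 1 out of 6 subjects experiences a DLT".

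**The concern.** The text and the table disagree on the size of the expansion (27 or 30) and on where it applies (the MTD at any level, or level 4). Neither number is made conditional on how many patients were treated at that level first.

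There is also a gap in the enrolment rules. A second group of three is added only after a DLT or on de-escalation. After 0/3 the instruction is to move up, but level 4 has no level above it. Section 4.2 adds nothing on this. The six-subject MTD definition implies a second three, yet no rule enrols them.

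The number at the MTD fixes the cutoff for the AGE-response test and its power. Section 3.3 makes registration and dose-level assignment central, so the risk is not that sites diverge. The central unit itself has two expansion numbers to work from.

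**Working it through.** **Inputs.** From Section 10.2: expansion 27, n = 33, p0 = 0.25, p1 = 0.50, one-sided alpha 0.05, exact binomial test, stated power 0.88, cap 54. From the Section 10.1 table: 3 (+3) at every level, and +30 at level 4.

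**Step 1. The plan's own power.** The cutoff c is the smallest value with P(X ≥ c | n, 0.25) ≤ 0.05, and power is P(X ≥ c | n, 0.50). At n = 33, c = 13, the size is 0.0484 and the power is 0.919. The stated 0.88 is not reproduced.

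A normal approximation with null variance for the critical value and alternative variance for power is

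power = Φ[(0.25√n − z√(0.25 × 0.75)) / 0.5].

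- n = 33, z = 1.645: (1.436 − 0.712)/0.5 = 1.448, power 0.926.
- n = 33, z = 1.960 (one-sided 0.025): (1.436 − 0.849)/0.5 = 1.175, power 0.880.
- n = 27, z = 1.645: (1.299 − 0.712)/0.5 = 1.174, power 0.880.

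At n = 33 and one-sided 0.05, using the alternative variance throughout gives 0.890. The exact test at n = 36 with cutoff 15 (size 0.021) gives 0.879. So 0.88 can be reached from n = 27, 33 or 36 by methods or alpha levels that the plan does not describe. It cannot be used to infer the intended expansion size.

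**Step 2. Number at the MTD under each reading.**

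| Reading | n | Cutoff | Size | Power |
|---|---|---|---|---|
| 6 + 27 (text, six at the MTD) | 33 | 13 | 0.0484 | 0.919 |
| 3 + 30 (table, three at level 4) | 33 | 13 | 0.0484 | 0.919 |
| 6 + 30 (table, six at level 4) | 36 | 14 | 0.0461 | 0.934 |
| 3 + 27 (text, second three not added) | 30 | 13 | 0.0216 | 0.819 |

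The drop at n = 30 is partly discreteness. A cutoff of 12 would give power 0.900, but its size of 0.0507 just exceeds 0.05.

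**Step 3. Maximum accrual.** Six at each of levels 1 to 4 is 4 × 6 = 24. Then 24 + 27 = 51 and 24 + 30 = 54, so the cap equals the table's total. If de-escalation can continue to level -1 (an assumption), escalation could use 5 × 6 = 30 patients, giving 30 + 27 = 57 or 30 + 30 = 60. Both exceed the cap.

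**Step 4. How often the uncovered case could arise.** The documents give no DLT rate, so I assume a constant rate p at every level. The chance of 0/3 at all four levels is (1 − p)^12:

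| p | 0.01 | 0.05 | 0.10 | 0.20 |
|---|---|---|---|---|
| (1 − p)^12 | 0.886 | 0.540 | 0.282 | 0.069 |

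This is a lower bound on reaching 0/3 at level 4, because Section 10.1 does not state what follows a 1/6 result at a lower level. It is the chance of meeting the uncovered case, not the chance of ending with n = 30.

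**The case against.** The best defence is that the intended size is stated. Section 10.2 says 33, and 6 + 27 and 3 + 30 both reach it. Expansion starts only once the MTD is established, and the MTD is defined on six, so a level with three treated does not yet qualify and n = 30 should not occur. The cap is only a ceiling, and 54 can also arise with 27: three at level 4, six at each of levels 3, 2, 1 and -1, then 3 + 24 + 27 = 54. No response cutoff is written into the plan, and an exact test works at whatever n is observed. Missing day 85 specimens could shift n just as much (exact power 0.892 at n = 32 and 0.859 at n = 31). The endpoint is secondary.

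Much of this stands. The reading 6 + 27 is the most coherent, n = 30 follows only from a literal reading of the enrolment rules, and 54 as a ceiling does not contradict 27. It does not remove the conflict. The two routes to 33 need different numbers treated first, and neither 27 nor +30 is tied to that number. If six are treated and the table is followed, n is 36. If the MTD is below level 4, the table shows no expansion at all. The path that gives 54 with 27 is not the maximum on its own assumption, since 57 is then possible. Attrition adds to uncertainty about n but is no reason to leave the planned n ambiguous.

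**Conclusion.** The concern holds. The plan gives two expansion sizes, and it has no enrolment rule for 0/3 at level 4 to match its six-subject MTD definition. Depending on the reading, 30, 33 or 36 patients are at the MTD, with exact power of 0.82, 0.92 or 0.93. The stated 0.88 is not the exact one-sided power at 33; it understates it by about four points, which is conservative.

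The consequence is moderate. AGE response is a secondary objective under Section 2.3, the definition of the MTD does not depend on 27 or 30, and power is at least 0.82 throughout. The power figures assume that every patient at the MTD has an evaluable change to day 85. The points should be corrected before expansion opens, so that n and cutoff are settled before the AGE results are seen.

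**What to change.** Before expansion opens:

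1. State one expansion number in the Section 10.2 text and the Section 10.1 table, attached to whichever level is the MTD and not to the level 4 row.
2. Reconcile the enrolment rule after 0/3 at level 4 with the six-subject MTD definition in Sections 2.2 and 10.1.
3. Restate the number at the MTD with its exact cutoff, size and power. For 6 + 27 these are n = 33, cutoff 13, size 0.048 and power 0.92.
4. Restate maximum accrual to match and say whether level -1 is counted. For 6 + 27 it is 51 over levels 1 to 4, or up to 57 if de-escalation can fill level -1 as well.

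If 6 + 27 was meant, the cost is protocol wording only. Against a 3 + 27 reading, treating six at level 4 adds three patients and possibly one more 28-day DLT window before expansion. Choosing 6 + 30 adds a further three patients.

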9 DATA SAFETY MONITORING

9.1 Responsible Individuals and Organizations.

The Principal Investigator will be responsible for monitoring the safety and efficacy of the trial, executing the DSM plan, and complying with all reporting requirements. This will be accomplished under the oversight of the HCC DSMC.

The HCC DSMC is responsible for monitoring data quality and patient safety for all interventional IITs at HCC. The HCC DSMC will have oversight of this protocol. The HCC DSMC will meet at a minimum on an annual basis to discuss the investigator-initiated trial. Also, the IIT will be audited by the DSMC auditor or external agency at least once a year.

The DSMC reviews all IRB reportable serious adverse events, monitoring/ auditing reports, and protocol deviations and has the authority to recommend closure and/or suspension for trials on which there are safety or trial conduct issues and may submit recommendations for corrective actions. The DSMC recommendations for modifications to the trial (if requested) are forwarded to the principal investigator. The principal investigator is notified of this recommendation in order that he/she may alert all investigators involved in the trial with regard to the potential action. At this time the principal investigators may submit to the DSMC additional information that could affect the Committee's decision.

All IRB reportable serious adverse events, monitoring/ auditing reports will be reviewed by the HCC DSMC for review during the DSMC monthly meetings. The SIS Unit will forward the event report to the HCC DSMC so that the information can be reviewed at the next available DSMB meeting. During the DSMB review, the DSMB can make recommendations for any further study action. The SIS Unit will maintain a copy of the DSMB approval letters for each event review within this study's central file.

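### Section 10.2 recruits 27 more patients at the MTD partly to define toxicity, but states no analysis of their DLTs, no DLT-based referral to the DSMC and no step to confirm or reconsider the MTD

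*Combined protocol and SAP*

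**What the plan says.** The primary objective (section 2.2) is the MTD: "The MTD will be defined as the dose that produces no more than 1 dose-limiting toxicity (DLT) in 6 subjects". Section 10.1 repeats the definition, "The MTD will be defined as the dose at which no more than 1 out of 6 subjects experiences a DLT", and sets out how it is reached: "The investigators will use a 3+3 design for assignment to cohorts". The DLT window is short: "Dose-limiting toxicities (DLT) will be defined only in the first 28 days of therapy". The one explicit de-escalation rule belongs to the escalation phase: "If two DLTs occur in the first 3 patients in a dose level, then dose will be de-escalated".

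The expansion opens only after the MTD has been established. Section 10.2 then states that "27 additional subjects will be recruited at that dose level to better define toxicity and changes in AGEs". The rest of 10.2 deals with AGE change: the binary 30% reduction endpoint, its exact test, paired comparisons, race strata and regression. Toxicity is not mentioned again.

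On oversight, section 9.1 makes the principal investigator responsible for safety monitoring under the DSMC. It adds that "The DSMC reviews all IRB reportable serious adverse events, monitoring/ auditing reports, and protocol deviations". Reportable SAEs and monitoring or audit reports go to monthly meetings, the trial itself is discussed at least once a year, and the committee may recommend suspension or closure. Section 4.4 has discontinuation rules for the individual patient. Appendix A schedules toxicity assessment by phone on days 14, 29 and 57 and at the day 85 visit.

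**The concern.** Better definition of toxicity is one of two stated purposes of the expansion, yet it has no analysis attached. The trial's primary conclusion is fixed before any of the 27 is treated. With 6 + 27 = 33 patients at the dose, 27/33 = 82% of the DLT information arrives after the declaration, and the plan does not say how it bears on the MTD.

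The general oversight does not clearly close this gap, because DLTs and SAEs are defined on different bases. A DLT (section 10.1) depends on grade: hypophosphatemia of grade 3 or above, or one of five listed gastrointestinal toxicities at grade 3 or above that the investigator attributes to chitosan and that has not improved or resolved by 7 days. An SAE (section 8.1) depends on outcome, such as death, threat to life, hospitalization or disability. A laboratory DLT or persistent grade 3 bloating may meet none of those criteria, so a run of DLTs need not reach the DSMC's monthly review.

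At stake are the reliability of the declared MTD and how soon an unexpectedly high DLT rate in the expansion would be formally examined.

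**Working it through.** The plan states no figure for toxicity monitoring, so there is none to reproduce. Inputs from the documents: at most 1 DLT in 6 (2.2, 10.1); the 3+3 rule (10.1); 27 expansion patients (10.2). The true DLT rate p is not in the documents; it is assumed, with a range shown.

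**1. Precision at declaration.** Exact (Clopper-Pearson) 95% intervals: 0/6 gives 0% to 45.9%; 1/6 gives 0.4% to 64.1%.

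**2. Chance that a single dose passes.** The 3+3 step is passed with 0/3, or with 1/3 followed by 0/3: (1−p)³ + 3p(1−p)²·(1−p)³ = (1−p)³ + 3p(1−p)⁵. If all 6 patients must be observed, the chance is (1−p)⁶ + 6p(1−p)⁵.

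- p = 0.30: 0.343 + 0.151 = 0.49; on a full six, 0.42.
- p = 0.40: 0.216 + 0.093 = 0.31; on a full six, 0.23.

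These are pass probabilities at one dose, not the chance that the whole escalation selects that dose.

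**3. Expected DLTs in the expansion.** 27p: 5.4 at 20%, 8.1 at 30%, 10.8 at 40%.

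**4. Could the pooled data contradict the declaration?** Yes. With 11 DLTs in 33 patients, the exact 95% interval is 18.0% to 51.8%, wholly above 1/6 = 16.7%. Section 10.2 does not say what would follow.

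**5. What a referral rule could do (illustration only).** Take 1/6 as the reference rate and a Beta(0.5, 1.5) prior. Refer when the posterior probability that the rate exceeds 1/6 is above 0.90, with looks when 12, 18, 24 and 30 patients in total have been treated at the dose. With x DLTs in n patients the posterior is Beta(0.5 + x, 1.5 + n − x). The smallest x that crosses 0.90 is 4, 6, 7 and 8 at the four looks. The exact recursion starts from 6 patients with at most 1 DLT:

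| True DLT rate | Probability of referral |
|---|---|
| 10% | 1% |
| 1/6 | 10% |
| 20% | 20% |
| 30% | 61% |
| 40% | 90% |

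If every referral ended accrual, expected expansion DLTs at a true 40% would fall from 10.8 to 5.5. Under the plan as written, the probability of a prespecified DLT-based referral is zero at every rate.

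**6. Is the DLT count complete?** Section 10.1 counts hypophosphatemia as a DLT within 28 days. Appendix A schedules phosphorus at screening, day 1 and day 85/end of study only. A patient who stays on study therefore has no scheduled post-dose phosphorus measurement inside the DLT window.

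**The case against.** A 3+3 followed by a fixed expansion under committee oversight is a legitimate design choice. Safety is not unwatched: the investigator monitors it, the DSMC can recommend suspension or closure, toxicity is assessed at scheduled contacts for every patient, and section 4.4 removes a patient whose grade 3-4 toxicity does not resolve. Section 1.6.4 cites 371 patients treated with chitosan at up to 5,250 mg daily, with no reported SAEs or grade 3-4 events. The highest level here is 2 × 2,000 = 4,000 mg daily. Against that record, a 40% rate of attributable, persistent grade 3 toxicity is an extreme case. The prior, cut-off and looks in the illustration are also choices; the protocol does not itself call 1/6 a tolerated rate.

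Most of this stands and limits the point. A reader might infer that expansion DLTs trigger no review at all. Sections 9.1 and 4.4 and Appendix A contradict that; what is missing is review tied to DLT counts. A reader might also infer that the MTD cannot change after the expansion, so that a clearly too-toxic dose would have to be reported as the MTD. The plan is silent on this and forbids nothing.

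The objection does not supply an analysis for a stated purpose of the expansion. The prior experience is reassuring but incomplete: section 1.6.4 notes that three of the studies made no comment on toxicity. In Table 1 only two studies state doses above 4,000 mg daily: 18 patients for 8 weeks, and 7 for 12 days with no toxicity comment. If toxicity is as low as expected, the illustrated rule would almost never fire.

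**Conclusion.** The point holds as a gap in section 10.2: no stated DLT analysis, no prespecified DLT-based referral, and no procedure for confirming or revising an MTD that rests on at most 6 patients. It does not hold as a claim that safety goes unreviewed or that the MTD is locked.

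The size depends on the unknown DLT rate. At an assumed 30% to 40%, a dose would pass the 3+3 step with probability 0.49 to 0.31 (0.42 to 0.23 on a full six), and 8.1 to 10.8 DLTs would be expected in the expansion without a formal trigger. At 10%, only 2.7 would be expected and the gap would matter little. The calculations assume independent patients, a constant DLT rate and full ascertainment of DLTs; the phosphorus schedule puts the last in doubt. This is an inexpensive improvement, not a flaw that invalidates the design.

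**What to change.** Add a paragraph to section 10.2 that:

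- counts 28-day DLTs in all patients treated at the MTD dose, escalation and expansion together;
- reports the pooled rate with an exact 95% confidence interval;
- states that the MTD conclusion will be confirmed or reconsidered on those data;
- prespecifies DLT counts at a few looks that pause accrual and refer the data to the DSMC. The sponsor sets the tolerated rate and the boundary; the 4/6/7/8 example only shows what such a rule can achieve.

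Two reconciliations are needed for the count to be well defined. The 28-day hypophosphatemia DLT must be reconciled with the phosphorus schedule in Appendix A. The expansion size must also agree: 10.2 says 27, while the dose table in 10.1 shows +30 at level 4. Section 10.2 also says "The maximum number of patients that can be accrued is 54", which equals 4 × 6 + 30; 4 × 6 + 27 gives 51.

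The cost is the paragraph and up to four brief looks, each needing a complete 28-day window for the patients counted. In the illustration, the chance of an unneeded referral is about 10% if the true rate is exactly 1/6 and 1% if it is 10%. Referral is not automatic stopping.
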